Procedure Afternoon Session	Cocaine Self Administration Depart from CRS			Three Doses of Cocaine (NexFin monitoring) Cardiovascular & Subjective Ratings Cardiac Biomarkers (4-6 hrs from last dose) Depart from CRS	Cocaine Self Administration Impulsivity Testing Depart from CRS
Study Drug	Placebo 8:00 a.m., Lorcaserin 10mg p.m. prior to departure or Placebo 8:00 a.m., Placebo p.m. prior to	Placebo 8:00 a.m., Lorcaserin 10mg p.m. prior to departure or Placebo 8:00	Placebo 8:00 a.m., Lorcaserin 10mg p.m. prior to departure or Placebo	Placebo 8:00 a.m., Lorcaserin 10mg p.m. prior to departure, or Placebo 8:00 a.m., placebo p.m. prior to departure	Placebo 8:00 a.m.

	departure	a.m., placebo p.m. prior to departure	8:00 a.m., placebo p.m. prior to departure		
--	-----------	--	---	--	--

Study Day	Day 8	Day 9	Day 10	Day 11	Day 12
Study Visit	Eight	Nine	Ten	Eleven	Twelve
Procedure Morning Session	Arrive at IDAS ECG	Arrive at IDAS ECG	Arrive at CRS ECG 10mg Cocaine for PK, Lorcaserin blood levels	Arrive at CRS ECG Cocaine Self Administration	Arrive at IDAS ECG Impulsivity Testing
Procedure Afternoon Session			Three Doses of Cocaine (NexFin monitoring) Cardiovascular & Subjective Ratings Cardiac Biomarkers (4-6 hrs from last dose) Impulsivity Testing Depart from CRS	Cocaine Self Administration Depart from CRS	Physical exam
Study Drug	Lorcaserin 10mg 8:00 a.m., Lorcaserin 10mg p.m. prior to departure. or Placebo 8:00 a.m., placebo p.m. prior to departure	Lorcaserin 10mg 8:00 a.m., Lorcaserin 10mg p.m. prior to departure or Placebo 8:00 a.m., placebo p.m. prior to departure	Lorcaserin 10mg 8:00 a.m., Lorcaserin 10mg p.m. prior to departure or Placebo 8:00 a.m., placebo p.m. prior to departure	Lorcaserin 10mg 8:00 a.m. or Placebo 8:00 a.m.,	

Self-Administration Session (Days 3, 7, and 11)

On days 3, 7, and 11, subjects participate in two self-administrative sessions and will make six choices for cocaine or \$5. The first session will begin at 10 am and the second at 1 pm (see Table 3 below), with each session being 2.5 hours long.

Table 3. Schedule of Cocaine Self Administration Procedure

Time	Choices	8 patients	8 patients
10:00 am	Baseline: VAS, BP/HR, EKG		
10:20 am	Choice 1	0 mg cocaine IV or \$ 5	25 mg cocaine IV or \$ 5
10:35 am	Choice 2	0 mg cocaine IV or \$ 5	25 mg cocaine IV or \$ 5

10:50 am	Choice 3	0 mg cocaine IV or \$ 5	25 mg cocaine IV or \$ 5
11:05 am	Choice 4	0 mg cocaine IV or \$ 5	25 mg cocaine IV or \$ 5

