Children as defined by NIH (age 18-21 years) will be included in this research. The incidence of severe cocaine abuse/dependence is relatively small in the population of youth less than 18 years old. From a safety perspective, risks of exposure to the proposed study medication and cocaine administration in substance-dependent children under 18 have not been established.

Analysis of Primary Endpoint

1. Safety: Heart rate (HR) and blood pressure (BP) measures during saline infusions will be compared to HR and BP after each cocaine infusion (20 mg and 40 mg doses). Changes in HR and BP induced by cocaine infusion along with lorcaserin will be compared to those without lorcaserin, by cocaine dose level (20 mg and 40 mg doses), using repeated measures analysis of variance (ANOVA). Changes in ECG readings during saline infusion as compared to those taken during cocaine infusions will be reported as summary statistics. Adverse event data will be compiled for lorcaserin and placebo cohorts and presented as summary statistics.
2. Cocaine Self-administration: Repeated measures ANOVA with cocaine dose (0mg, 25mg) and lorcaserin dose (0mg, 10mg, 20mg) as within subject factors will be used to examine differences in mean cocaine choice selection. In addition, a Bayesian analysis will be carried out as described below.
3. Subjective response to cocaine: Subjective response measures (VAS) obtained during saline infusions will be compared between lorcaserin and placebo subjects to those during cocaine infusions by cocaine dose level to determine the extent to which these measures are modified by the administration of lorcaserin using repeated measures ANOVA.
4. Cocaine PK: Plasma concentration-time profiles of cocaine after cocaine infusion during placebo administration (Day 2) will be analyzed to obtain pharmacokinetic parameter estimates of cocaine (Tmax, AUC, apparent t_{1/2}, CL) by individual. These parameters will be compared within subjects on sessions with lorcaserin (Day 6 and 10).

Analysis of Secondary Endpoints

Response inhibition: Commission errors on the IMT will be compared between lorcaserin and placebo subjects to determine the extent to which this measure is modified by the administration of lorcaserin using repeated measures ANOVA.

Safety and tolerability data will be summarized by treatment group.

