Adverse event rates will be coded by body system and MedDra classification term. Adverse events will be tabulated by treatment group and will include the number of patients for whom the event occurred, the rate of occurrence, and the severity and relationship to study drug.

Interim Analysis

When approximately 50% of patients have completed the study, an interim analysis for safety will be conducted by the DSMB. Serious adverse events will be monitored by the committee on an ongoing basis throughout the study.

Sample Size and Randomization

This project requires a final sample size of 18 subjects (Six subjects assigned to Group A (placebo) and 12 subjects assigned to Group B (active lorcaserin)). This sample size for effect of lorcaserin on cocaine self-administration was based on previous research showing effects of medication on human cocaine self-administration (Hart et al, 2008). In an effort to increase the power of the study, a Bayesian approach will also be utilized that incorporates information from previous studies. This approach will use a Bayesian hierarchical model with subject at the lowest level of the hierarchy and treatment group at the second level. This model is analogous to the repeated measures ANOVA except that prior information will be introduced. Since many similar studies have been conducted with cocaine users and the same outcome measures we will assign an

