informative prior distribution on the control group where the mean and standard deviation are educated guesses from the information provided in previous study of Hart et al. (2008). For the treatment group we will assume a priori no change in the mean from the control group and the standard deviation are similar to those as the experimental group of the study by Hart et al. (Hart et al, 2008). The model will be calculated using standard Markov Chain Monte Carlo (MCMC) packages such as WinBUGS, OpenBUGS, JAGS or MCMCpack in R. Because MCMC sampling techniques are being employed the quality of the samples from the posterior distribution will be checked using trace plots, effective sample size, potential scale reduction factor and Hellinger distances (for more on Bayesian analyses and MCMC sampling see (Gelman et al, 2013). As necessary techniques such as discarding burn-in samples, thinning and over-disperse starting points will be employed in order to obtain a set of samples from the posterior distribution that have an effective sample size of 10,000 on all parameters. All inferences will be made from this set of samples from the posterior distribution.

To calculate the power for the acute effects of the study three analyses are considered using the paired differences of subjects at baseline and acute time points. A two-sample test on the means is performed using: Wilcoxon test (non-parametric), T-test (parametric) and a Bayesian (parametric) approach. While from a

n1	Test	Percent Change				
		Low (10%)	Medium (25%)	High (50%)	75%	100%
4	T-test	0.116	0.448	0.955	0.998	1
	Wilcoxon	0.044	0.242	0.855	0.992	1
	Bayesian	0.249	0.689	0.992	1	1
6	T-test	0.138	0.528	0.981	0.999	1
	Wilcoxon	0.079	0.357	0.941	0.997	1
	Bayesian	0.308	0.782	0.994	1	1
8	T-test	0.116	0.588	0.986	1	1
	Wilcoxon	0.096	0.495	0.956	1	1
	Bayesian	0.309	0.803	0.999	1	1
Wilcoxon and Bayesian Power are based off of 1,000 Monte Carlo simulations.						

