Bayesian paradigm the notion of power does not exist in the traditional sense, one can create a decision rule and loss function in such a way that the associated risk is analogous to the notion of power. To understand the power of each of the methods a Monte Carlo study was performed utilizing 1,000 separate datasets for likely effect sizes and sample sizes. The power was calculated as the proportion of datasets in which the test “rejected” the null hypothesis. The table below gives the power for each test across percent change in effect size and control group sample sizes, here the treatment group sample size was $n_2 = 12$. Based on the table at left, an n of 6 was chosen as the sample size for the placebo group.

DATA COLLECTION, RETENTION AND MONITORING

Data Collection Instruments

The Investigator will prepare and maintain adequate and accurate source documents designed to record all observations and other pertinent data for each subject treated with the study drug.

Study personnel at each site will enter data from source documents corresponding to a subject’s visit into the protocol-specific paper CRF when the information corresponding to that visit is available. Subjects will not be identified by name in the study database or on any study documents to be collected by the Sponsor (or designee), but will be identified by a subject number.

The Investigator is responsible for all information collected on subjects enrolled in this study. All data collected during the course of this study must be reviewed and verified for completeness and accuracy by the Investigator.

Data Management Procedures

The data will be entered into a REDCap database. The Data Management group will be responsible for data processing, in accordance with procedural documentation. Database lock will occur once quality assurance procedures have been completed.

All procedures for the handling and analysis of data will be conducted using good computing practices meeting FDA guidelines for the handling and analysis of data for clinical trials.

Data Quality Control and Reporting

After data have been entered into the study database, a system of computerized data validation checks will be implemented and applied to the database on a regular basis. The study database will be updated in accordance with the resolved queries. All changes to the study database will be documented.

Archival of Data

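### Self-administration has two analyses and two on-drug days, and the plan does not say which analysis, which day or what Bayesian threshold decides

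*Combined protocol and SAP*

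**What the plan says.** Analysis of Primary Endpoint, item 2 (repeated in the synopsis and under Criteria for evaluation), enters cocaine dose (0, 25 mg) and lorcaserin dose (0, 10, 20 mg) in a repeated measures ANOVA "as within subject factors will be used to examine differences in mean cocaine choice selection". It lists no treatment-group factor. It then adds: "In addition, a Bayesian analysis will be carried out as described below".

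Sample Size and Randomization gives the reason for the second analysis: "In an effort to increase the power of the study, a Bayesian approach will also be utilized that incorporates information from previous studies". That model has subject at the lowest level and treatment group at the second. The paragraph on MCMC sampling ends: "All inferences will be made from this set of samples from the posterior distribution". On a decision rule, the section says only that "one can create a decision rule and loss function in such a way that the associated risk is analogous to the notion of power". No rule or threshold follows.

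The same section computes power "using the paired differences of subjects at baseline and acute time points", as a two-sample test with 12 lorcaserin subjects and 4, 6 or 8 placebo subjects. Six were chosen.

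The Self-Administration Session section sets three assessment days: "On days 3, 7, and 11, subjects participate in two self-administrative sessions". By the visit schedule, Day 3 sessions come before the first lorcaserin dose that evening. Day 7 follows the 10 mg daily period, and Day 11 falls in the 10 mg twice daily period.

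**The concern.** The plan describes three objects for one outcome: a within-subject ANOVA over dose levels, a Bayesian model at group level, and a powered two-sample comparison of a single change. They need not give the same answer.

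The within-subject dose factor has a further difficulty. Group A receives placebo throughout and so cannot supply the 10 and 20 mg levels. In Group B each dose level coincides with one day (3, 7, 11). Without a group term, a dose effect cannot be told apart from a change over days. The Bayesian model and the power calculation do use the placebo group.

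The Study Overview says the data will inform go/no-go decisions on phase II. If the analyses or the two days differ, the text does not say which result is the trial's answer on the outcome that set its size. The choice could be made after the results are seen.

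**Working it through.** **Inputs.** The power table in Sample Size and Randomization, at 6 placebo and 12 lorcaserin subjects. T-test: 0.138, 0.528, 0.981, 0.999 at 10%, 25%, 50% and 75% change. Bayesian: 0.308, 0.782, 0.994, 1. The plan gives no alpha, sidedness, SD, control mean, prior values or posterior threshold.

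**1. Reproducing the table.** The Bayesian row cannot be reproduced. For the t-test row, assume two-sided alpha 0.05 and a standardised effect d proportional to the percent change. With 16 df the noncentrality is d / √(1/6 + 1/12) = d / 0.5 = 2d. Solving for the stated 0.528 at 25% gives d = 1.08, that is d = 4.32 × change. The other n1 = 6 values then follow:

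| Change | d | Computed | Stated |
|---|---|---|---|
| 10% | 0.432 | 0.129 | 0.138 |
| 25% | 1.08 | 0.528 (fitted) | 0.528 |
| 50% | 2.16 | 0.982 | 0.981 |
| 75% | 3.24 | 1.000 | 0.999 |

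One-sided 0.05 fits less well (0.169 against 0.138 at 10%). With the same two-sided slope, some cells at other sizes do not match: 0.414 against 0.448 (n1 = 4, 25%), 0.146 against 0.116 (n1 = 8, 10%) and 0.610 against 0.588 (n1 = 8, 25%). A two-sided 5% t-test is therefore a plausible reading of the n1 = 6 row, but the documents do not confirm it.

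**2. How often the two methods must differ.** If they reject with probabilities b and t, the chance that exactly one rejects is at least |b − t| and at most min(b + t, 2 − b − t). This needs no assumption about their correlation.

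| Change | At least | At most |
|---|---|---|
| 10% | 0.308 − 0.138 = 0.170 | 0.308 + 0.138 = 0.446 |
| 25% | 0.782 − 0.528 = 0.254 | 2 − 1.310 = 0.690 |
| 50% | 0.994 − 0.981 = 0.013 | 2 − 1.975 = 0.025 |
| 75% | 1 − 0.999 = 0.001 | 2 − 1.999 = 0.001 |

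The Bayesian values come from 1,000 simulations, so 0.782 has a standard error of √(0.782 × 0.218 / 1000) = 0.013. The gap at 25% is far larger than that.

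**3. Choice of day.** Suppose either Day 7 or Day 11 could count at two-sided 5% (assumed). The false-positive rate is 5% if the two days always agree, and 1 − 0.95² = 9.75% if they are independent. Simulating two correlated t-tests (6 v 12 subjects, 100,000 runs) gives about 9.1%, 8.4% and 7.2% at assumed correlations of 0.5, 0.7 and 0.9.

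**The case against.** **Flat contradiction.** A reader might infer that one section makes ANOVA the analysis and another overrides it by drawing all inferences from the posterior. The text does not support that. The sentence closes a paragraph on burn-in, thinning and effective sample size, and most naturally covers inferences within the Bayesian analysis. Elsewhere that analysis is described as an addition. What remains is the missing ranking.

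**Two planned tests at 5%.** This too goes beyond the text. Lorcaserin dose enters one ANOVA as a three-level factor, so its effect is a single omnibus test. The 5% to 9.75% range applies only if separate day comparisons are allowed to count. However, the omnibus test names no day or placebo contrast, and it does not govern the Bayesian analysis.

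**Four independent chances.** A reader might also multiply two methods by two days. That fails: both methods use the same 18 subjects, the plan calls the Bayesian model analogous to the ANOVA, and the Bayesian error rate is not stated.

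**Proxy and selection of effect sizes.** The disagreement rates compare the Bayesian rule with a two-sample t-test, not the planned ANOVA, whose power is not given. No design effect is named, and at a 50% change or more the methods almost always agree. Both limits stand.

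**A later SAP.** Statistical Methods and Considerations promises a detailed SAP before the final data are analysed. It could settle the point, but it is not in the documents. The text requires it before analysis rather than before unblinding, and the Blinding section opens the blind once the database is locked.

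**Early phase.** This is an 18-subject phase 1b/2a study with no defined success criterion. That limits how serious the gap is, but does not close it.

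**Conclusion.** The concern holds as a gap in specification: no leading analysis, no decisive on-drug day and no posterior threshold for the outcome that sized the trial. It should be corrected.

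Its size depends on the true effect. The methods differ in at least 17% of trials at a 10% change and 25% at a 25% change, but only about 1% at 50%. These figures rest on the plan's own powers and on the t-test standing in for the ANOVA. The 5% to 9.75% range rests on an assumed alpha of 5% and on either day being allowed to count.

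Because the Bayesian rule's false-positive rate is not reported, its higher power cannot be compared with the t-test at equal error. The missing threshold therefore matters in its own right. The gap itself is read from the text and does not depend on these calculations.

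**What to change.** Before unblinding, amend item 2 and carry the change into the SAP:

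- Name one decisive contrast that has the form of the power calculation: the lorcaserin-minus-placebo difference in change from Day 3 to Day 11 in choices in the 25 mg session. Day 11 is a proposal, since the documents favour neither day. What matters is that one day is fixed. The comparison with placebo separates treatment from day.
- Name one analysis of that contrast as primary. State its alpha and sidedness if frequentist, or its prior values and posterior threshold if Bayesian.
- Label Day 7 and the other analysis as supportive.
- In Sample Size and Randomization, say that the sentence on all inferences refers to the Bayesian analysis only, unless that analysis is chosen as primary. State which day the acute time point means.

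The cost is protocol and SAP wording, with no added subjects or procedures. The sponsor gives up relying on whichever method or day looks better.

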Each pill bottle of study drug will be labeled with the required FDA warning statement, the protocol number, a treatment number, the name of the study physician, and directions for patient use and storage.

Administration of Study Drug

Dosage/Dosage Regimen

If subjects meet inclusion criteria, they will be seen both in the hospital and at IDAS clinic for a total of 12 active study days and monitoring procedures will be in place to detect drug and alcohol use and assess for adverse events at each visit. In addition, the hospital cocaine administration procedures will reduce the likelihood of increased cocaine craving after cocaine administration. Subjects will undergo procedures as described below. Subjects will not be allowed to smoke cigarettes, as smoking is not allowed in the hospital or anywhere on the VCU campus. Subjects will have the option to use a nicotine patch dosed based on the amount of daily cigarettes smoked. Subjects will not be allowed to leave the CRS Unit nor receive visitors during their study visits. Subjects who are unable to comply with these restrictions will be dropped from the study. After a screening cocaine infusion to determine safety, eligible subjects will be randomized to Group A –placebo only or Group B –placebo followed by an ascending dose of lorcaserin. Six subjects will be assigned to Group A (placebo) and 12 subjects will be assigned to Group B (active lorcaserin).

Study Drug Dosage: Lorcaserin will be 10mg once daily increasing to 10mg twice daily.

Outcome Measures: The primary outcome measures are adverse events, cardiovascular responses (Heart rate (HR), blood pressure (BP), ECG measurements, subjective response to cocaine, cocaine self-administration, and cocaine blood PK. Secondary outcome measures will be impulsivity as measured by the immediate memory task (IMT).

- 1) Days 1-2: All subjects will be seen on the CRSU. All subjects will receive placebo on days 1-2 in a single blind fashion. Vital signs including heart rate, blood pressure and respiration rate will be obtained after placebo administration. Days 1-2 will be single-blind placebo, whereas all remaining study days will be double-blind. All subjects will leave the CRSU at the end of each study day.

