- 2) Days 3-6: All subjects will be seen on the CRSU on days 3 and 6, and at the IDAS clinic on days 4 and 5. On days 3-6, subject group A will receive one placebo pill twice daily, and group B will receive one placebo pill in the morning and one matching lorcaserin 10 mg pill in the evening, for a total dose of 10 mg daily. ECG with QTc will be performed daily. If the QTc is prolonged greater than 30ms over baseline lorcaserin dosage will be held.
- 3) Day 7: All subjects will receive one placebo pill in the morning in single blind fashion. Following Cocaine Self-administration sessions and impulsivity testing the subjects will leave the unit.
- 4) Days 8-10: All subjects will be seen at the IDAS clinic on Days 8 and 9 and subjects in group B will have a blinded dosage increase to 10 mg of lorcaserin twice daily for Days 8-11 (Days 10 and 11 will take place at the CRSU). Vital signs including heart rate, blood pressure and respiration rate will be obtained before placebo/lorcaserin administration. ECG with QTc will be performed daily under the supervision of a study physician. If the QTc is prolonged greater than 30ms over baseline lorcaserin dosage will be held.
- 5) Day 11: All subjects will be seen on the CRSU and receive placebo/lorcaserin in the morning followed by the last cocaine self-administration session.
- 6) Day 12: Subjects will be seen at IDAS for study procedures.
- 5) Cocaine Infusion Sessions (Days 1, 2, 6, and 10): All subjects will undergo an ascending dose intravenous cocaine administration after admission on day 1 to ensure safety of later cocaine studies.

To assess the safety and subjective effects of cocaine in the presence of lorcaserin, subjects will receive ascending doses of intravenous cocaine (10 mg, 20 mg, 40 mg), with each cocaine administration separated by

one hour. In addition, 0 mg cocaine (saline) infusion will be randomly given after the first dose of cocaine in order to aid in blinding investigators and subjects to the order of drug administration. Infusions will be carried out hourly starting from 1 hour after placebo/lorcaserin for 4 times (on Day 1, 2, 6, and 10). An example dose by session diagram is shown below. Note that the 0 mg dose is randomly given after the first dose of cocaine. Monitoring will be continued for 1 hour after the last dose of cocaine.

Dose	Dose Session 1	Dose Session 2	Dose Session 3	Dose Session 4
1	10 mg Cocaine	10 mg Cocaine	10 mg Cocaine	10 mg Cocaine

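### The VAS (primary item 3) and IMT (secondary) analyses do not say how the pre-lorcaserin sessions are used or which contrast is tested, and they make no use of the pre-drug value as baseline

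*Combined protocol and SAP*

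**What the plan says.** In the combined protocol and SAP, Analysis of Primary Endpoint, item 3 says of the VAS scores taken under saline that they "will be compared between lorcaserin and placebo subjects to those during cocaine infusions by cocaine dose level". The method is repeated measures ANOVA, and the declared aim is to find how far lorcaserin changes the scores. Under Analysis of Secondary Endpoints, "Commission errors on the IMT will be compared between lorcaserin and placebo subjects", also by repeated measures ANOVA. The only structure named is group and, for VAS, saline against cocaine by dose. No day, phase, baseline or tested term is given.

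The dosing timeline is under Dosage/Dosage Regimen. "All subjects will receive placebo on days 1-2 in a single blind fashion". On Days 3-6 "group B will receive one placebo pill in the morning and one matching lorcaserin 10 mg pill in the evening", and there is a "blinded dosage increase to 10 mg of lorcaserin twice daily for Days 8-11". Infusion sessions are on Days 1, 2, 6 and 10. Appendix 1 marks IMT on Days 1, 4, 7 and 10.

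The neighbouring primary items do separate the two states. Item 1 compares responses with and without lorcaserin. Item 2 makes lorcaserin dose, including 0 mg, a within-subject factor. Item 4 sets Day 2 against Days 6 and 10.

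**The concern.** A subject in the lorcaserin group is not on lorcaserin at every session. Days 1 and 2 (VAS) and Day 1 (IMT) carry no information on the drug effect except as baseline. A repeated measures ANOVA on group and cocaine dose can be run with all sessions in the between-group comparison. Its null is then no group difference averaged over pre-drug and on-drug sessions. That test keeps its size when lorcaserin does nothing, but a real effect is diluted, and chance pre-drug differences between 6 and 12 subjects enter the estimate. The same wording also allows a group-by-day test, which is not diluted. The result of a primary outcome in 18 subjects could therefore turn on a choice that the plan does not make.

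**Working it through.** **The plan's own figures.** No power, SD or effect size is stated for VAS or IMT. The only power table (Sample Size and Randomization) concerns self-administration. For 6 placebo and 12 lorcaserin subjects the t-test row reads 0.138 / 0.528 / 0.981 / 0.999 at 10 / 25 / 50 / 75% change. Its SD, alpha and sidedness are not given. A back-solved SD of about 23 percentage points (pooled t, two-sided 0.05) returns 0.129 / 0.528 / 0.982 / 1.000. For scale only, with that SD fixed, multiplying the 25% effect by 0.75, 0.67 or 0.5 takes power from 0.53 to 0.33, 0.27 or 0.17.

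**Dilution.** With equally weighted sessions and an equal effect on every on-drug day, estimate / true effect = on-drug sessions / all sessions.

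- VAS, Days 1, 2, 6, 10: 2/4 = 0.50.
- VAS, Days 2, 6, 10: 2/3 = 0.67.
- IMT, Days 1, 4, 7, 10: 3/4 = 0.75.

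If the 10 mg effect were half the 20 mg effect (assumed), the pooled estimate as a share of the top-dose effect would be (0 + 0 + 0.5 + 1)/4 = 0.375 for VAS and (0 + 0.5 + 0.5 + 1)/4 = 0.50 for IMT.

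**Which term matters.** In data simulated for Days 1, 2, 6 and 10 with a true effect of 1.0, the group estimate was 0.508 without a day term and 0.508 with an additive one. An additive day term removes only what both groups share on a day. The group-by-phase coefficient was 1.01.

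**Power.** Assumptions, none of them from the documents: per-session SD 1 (for VAS, the SD of the cocaine-minus-saline contrast), lorcaserin effect 1.0 SD and equal on all on-drug days, compound symmetry with correlation r = 0.3 / 0.5 / 0.7, two-sided 5%. For 6 v 12, √(1/6 + 1/12) = 0.5.

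- Mean of k sessions: variance r + (1 − r)/k; noncentrality = estimate / (0.5 × SD), 16 df. Pooled VAS at r = 0.5: variance 0.625, SD 0.791, noncentrality 0.50/(0.5 × 0.791) = 1.26, power 0.22. Days 6 and 10 only: variance 0.75, noncentrality 1/(0.5 × 0.866) = 2.31, power 0.58.
- Change from one pre-drug session, with m on-drug sessions: variance (1 − r)(1/m + 1).
- Omnibus group-by-day test over k = 4 days: F on 3 and 48 df, noncentrality S / [0.25(1 − r)], where S is the sum of squared deviations of the daily effects from their mean (VAS 1.0, IMT 0.75).
- On-drug mean with one pre-drug session as covariate: residual variance r + (1 − r)/m − r² (VAS 0.56 / 0.50 / 0.36), 15 df. Power is from 100,000 simulated trials; runs of a few thousand scatter by about 0.02.

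| Analysis | VAS, r = 0.3 / 0.5 / 0.7 | IMT, r = 0.3 / 0.5 / 0.7 |
|---|---|---|
| Group effect, all four sessions | 0.28 / 0.22 / 0.19 | 0.53 / 0.43 / 0.36 |
| Omnibus group-by-day | 0.46 / 0.61 / 0.85 | 0.36 / 0.48 / 0.72 |
| On-drug days, no baseline | 0.64 / 0.58 / 0.53 | 0.73 / 0.63 / 0.56 |
| Change from one pre-drug session (Day 2; Day 1) | 0.45 / 0.58 / 0.80 | 0.49 / 0.63 / 0.84 |
| On-drug days, same session as covariate | 0.68 / 0.72 / 0.85 | 0.78 / 0.80 / 0.90 |

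Without Day 1, the pooled VAS test has power 0.40 / 0.34 / 0.29. Change from the mean of Days 1 and 2 gives 0.61 / 0.76 / 0.93 for VAS. That exceeds the Day 2 covariate at r = 0.5 and 0.7 because it uses two pre-drug sessions, but it needs the Day 1 screening session to be comparable with Day 2.

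**The case against.** A reader might infer that the plan counts pre-lorcaserin sessions as lorcaserin outcomes, so that the VAS effect is halved as written for want of a day term. The documents do not support this.

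- The text never says which days enter or which term is tested, so the dilution depends on a reading.
- IMT has no cocaine-dose factor and one administration per listed day, so test day is its natural repeated factor. A group-by-day term would then be available, and it is not diluted.
- The missing day term is not the cause, since an additive one changes nothing. What is missing is a group-by-phase contrast or a baseline.
- The half needs Day 1 in the VAS analysis. Dosage/Dosage Regimen describes Day 1 as a safety screen before randomisation, and Table 2 lists subjective ratings on Days 2, 6 and 10 only. Appendix 1 does record VAS on Day 1.
- Items 1, 2 and 4 separate the two states, and the power section works from paired differences from baseline, so a baseline reading may be intended. A detailed SAP is still to be written.
- Study Overview ties go/no-go decisions to the study's data as a whole, not to VAS.

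All of this stands, and it makes the bias conditional. It does not settle the analysis: item 3 and the IMT paragraph are the places where the separation is absent, and the comparison that they do name is between groups. The likely alternative, an omnibus group-by-day test, generally has less power than baseline adjustment under these assumptions (the two are level for VAS at r = 0.7). The promised SAP is where the correction belongs, but nothing in the current text secures it.

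**Conclusion.** The point holds as an unspecified contrast with an unused baseline, not as a demonstrated bias. If the group effect, or group by cocaine dose, is taken over all sessions, the lorcaserin effect shrinks by half for VAS, by a third if Day 1 is left out, and by a quarter for IMT. These fractions assume equal weights and equal effects on all on-drug days. That equality is doubtful: Days 6 and 10 differ in dose, Day 4 IMT comes shortly after the first capsule, and on Day 7 Group B has only a morning placebo, its last lorcaserin being on the Day 6 evening. Every power figure for VAS and IMT rests on assumed SDs, correlations and a 1.0 SD effect. On that footing, covariate adjustment beats both the pooled group test and the omnibus group-by-day test for IMT at all three correlations. For VAS it beats the pooled test throughout, and beats the omnibus test except at r = 0.7, where the two are about equal. The plan should be changed before the data are analysed.

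**What to change.** **VAS (item 3).** Define the lorcaserin effect as the Group B minus Group A difference in the cocaine-minus-saline contrast, at 20 mg and at 40 mg, on Day 6 and on Day 10, with the subject's own Day 2 contrast as covariate (ANCOVA or a mixed model). State that Days 1 and 2 are not outcome sessions.

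**IMT.** Use Days 4, 7 and 10 as outcomes and Day 1 as covariate. Report the group difference by day, because lorcaserin exposure differs between these days. Confirm the IMT days: Table 2 also lists impulsivity testing on Day 12, where Appendix 1 marks no IMT.

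Use covariate adjustment rather than change from a single baseline session, which loses power when between-session correlation is low (VAS at r = 0.3: 0.45, against 0.64 with no baseline at all). If repeated measures ANOVA is kept, base inference on the on-drug contrasts, not on a group or group-by-dose term averaged over days.

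The cost is analysis wording and one degree of freedom (16 to 15). The data are already scheduled for collection, and no study procedure changes.
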